5. Control Arm: Ingest a placebo tab orally with similar physical properties. This will coincide with or be implemented prior to the initiation of the induction of labor plan as delineated by the attending physician. The timing will be sensitive to the needs of the participant and the labor and delivery room staff.
6. Montefiore protocol for induction of labor:
 - a. 12w0d-23w6d: Misoprostol 400 micrograms vaginally every 3 hours for 5 doses.
 - b. 24w0d-28w6d: Misoprostol 400micrograms vaginally every 6 hours for 5 doses.
 - c. 29w0d and older: Misoprostol 25-50mcg vaginally every 4 hours for 4 doses OR 100mcg vaginally every 12 hours for 4 doses.
 - d. Induction methods and protocols will be at the discretion of the physician team and tailored to the clinical context.
7. Data: Patient data will be collected by the Labor and Delivery staff via electronic medical record or paper record that will be scanned into the electronic medical record. The investigators will use data abstraction tools to collect information such as time of medication administration, medications administered, time of delivery of fetus, duration of admittance to labor and delivery, and postpartum course, or complications from the electronic medical record.

2.2 Definitions:

1. Intrauterine Demise: Absence of fetal heart motion on bedside ultrasound; confirmed by two separate providers and the attending physician.
2. Mifepristone: A 19-nor-steroid derivative of norethindrone that competitively binds to progesterone and glucocorticoid receptors, with antagonist effect. Mifepristone administration is the standard of care when providing medical management for first and second trimester terminations/abortions as per the American Congress of Obstetricians and Gynecologists.
3. Induction of Labor: The use of medications and other techniques to induce contractions and cervical change with the goal of effecting delivery and evacuation of all uterine contents.

2.3 Protocol Amendments:

All amendments to the protocol by the primary research team will be delineated on handouts and distributed at participating Labor and Delivery Units at 8AM the following day. The same information

will be electronically mailed to resident physicians, attending physicians, physician assistants and nurse managers currently staffing the participating Labor and Delivery units.

III Drug Information

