4.1 Recruitment

Patients will be recruited at the time of admission to the Labor and Delivery units at the Montefiore Hospitals – Einstein Campus at Weiler and Montefiore North, at which there are approximately 60 and 30, respectively, fetal demises diagnosed annually. Firstly the diagnosis of fetal death will be ascertained as per the standards of the unit by the attending physician. The medical team will counsel the patient on the induction of labor plan. Based on inclusion and exclusion criteria potential participants will be informed about the research, offered the opportunity to voluntarily contribute, and trained research staff will complete the informed consent process. The timing of consent will be sensitive to the needs of the participant. The research and therefore voluntary aspect of care will be clearly delineated. After documentation of consent and discussion of the research as indicated the participants will be randomized to the intervention or control arm. Both groups will receive emotional and physical support with induction of labor as per practice guidelines and standard of care by Montefiore physicians, faculty and staff irrespective of participation or assignment.

Patients in the interventional arm will ingest 200mg tab of mifepristone orally. This will coincide with or be implemented prior to the initiation of the induction of labor plan as delineated by the attending physician. The timing will be sensitive to the needs of the participant and the labor and delivery room staff.

Similarly, patients in the control arm will ingest a placebo tab orally with similar physical properties without the active ingredient. This will coincide with or be implemented prior to the initiation of the

induction of labor plan as delineated by the attending physician. The timing will be sensitive to the needs of the participant and the labor and delivery room staff.

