4.4 Participant Timeline

1. The patient receives a diagnosis of intrauterine fetal demise at 20 weeks gestational age or greater.
2. Patient must meet inclusion and exclusion criteria of study.
3. Patient verbally consents to the delivery plan and is a candidate for induction at a Montefiore labor and delivery (Wakefield or Weiler-Einstien Hospitals).
4. Participants will be informed about the research, offered the opportunity to contribute, and trained research staff will complete the informed consent process.
5. After documentation of consent and discussion of the research as indicated the participants will be randomized to the intervention or control arm. Both groups will receive emotional and physical support with induction of labor as per practice guidelines and standard of care by Montefiore physicians, faculty and staff irrespective of participation or assignment.
6. With prior assignment based on the randomization scheme medications will be maintained in secure medical dispensing equipment consistent with Montefiore standards (labor and delivery Pyxis will be used). Medications will be individually placed in sequentially numbered, sealed opaque containers. Research team will source and dispense medication to participants.
6. Patient's labor course is routinely monitored and documented in EMR by all participating providers.

V Randomization

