Allocation methods will be variable block randomization (blocks of 2&6, by computer generated random number sequence. Best practices will be implemented to assure the maintenance of randomization and blinding. The randomization scheme will be kept at a separate secure research site and researchers will not have access to this scheme until the analysis phase, following completion of the data collection process and enrollment. The Montefiore research pharmacy will be involved in the storage, packaging, monitoring and utilization of both placebo and study medications. The placebo and study medications will be maintained in secure medical dispensing equipment consistent with Montefiore standards (labor and delivery Pyxis). Medications will be individually placed in sequentially numbered, sealed opaque containers with a unique participant identifier that will correspond with the patient identifier the participant receives upon enrollment. Participants, research staff, and the data collection and analysis teams will be blinded to contents of each pill. The mifepristone and placebo tablets will be obtained from Danco pharmacies where the placebo has been specifically developed to have similar physical properties to the mifepristone tablet.

VI Data Collection

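### No stratification by hospital or gestational-age band is specified, and the list structure for two hospitals is not stated, so balance on either factor is not ensured in 74 women

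*Combined protocol and SAP*

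**What the plan says.** Section V (Randomization) describes the method as follows: "Allocation methods will be variable block randomization (blocks of 2&6, by computer generated random number sequence". Packaging is described by "Medications will be individually placed in sequentially numbered, sealed opaque containers with a unique participant identifier", and custody by "The randomization scheme will be kept at a separate secure research site". Sections 4.4 and V place the drug in the labor and delivery Pyxis. No section names a stratification factor, and none says whether the numbered series is common to both units or separate for each.

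Two units recruit. Section 4.4, item 3, requires that the woman "is a candidate for induction at a Montefiore labor and delivery (Wakefield or Weiler-Einstien Hospitals"). Section 4.1 gives their volumes: "at which there are approximately 60 and 30, respectively, fetal demises diagnosed annually".

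Section 2.1, item 6, lists background misoprostol by gestational age:
- "12w0d-23w6d: Misoprostol 400 micrograms vaginally every 3 hours for 5 doses"
- "24w0d-28w6d: Misoprostol 400micrograms vaginally every 6 hours for 5 doses"
- "29w0d and older: Misoprostol 25-50mcg vaginally every 4 hours for 4 doses OR 100mcg vaginally every 12 hours for 4 doses"

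Item 6d then leaves methods to the physician team's discretion. Gestational age is confirmed before consent (section 2.1, item 2) and recorded at intake (section VI).

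Section 7.2 plans a two-sample t-test and a Wilcoxon rank sum test for time to delivery, with no term for hospital or gestational age. The only covariate control mentioned anywhere is in section 3.1, for medicines that affect the enzyme that metabolises mifepristone.

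**The concern.** Blocks of 2 and 6 keep the overall arm totals close. They do nothing for subgroups unless each subgroup has its own list. Gestational-age band and hospital are both known before randomisation, and the band sets the listed background induction, which acts on the same outcome as the study drug. With 37 women per arm, chance can put noticeably more women of one band, or of one hospital, into one arm. The planned primary tests would not correct for it. A reader of the results would then ask how much of the observed difference reflects case mix.

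There is also a practical gap. Numbered containers have to be stocked at two units that enrol in parallel, and the plan does not say how the series is divided. Whether the blocks still work within each hospital depends on that choice.

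**Working it through.** **1. The plan's own sample size.** Inputs from section 7.1: difference 4 h, SD 6 h, two-sided alpha 0.05, power 0.80.
- Normal formula: n per arm = 2 × (1.960 + 0.842)² × 6² / 4² = 2 × 7.849 × 36/16 = 35.3, so 36.
- The t-based calculation gives 36.3, so 37, which reproduces the plan's 37 per arm.
- Power at 37 per arm is 0.82 (normal) or 0.81 (t).

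**2. Size of the change in listed dose at 29w0d.** Per dose: 400/100 = 4, 400/50 = 8 and 400/25 = 16. The range is therefore 4- to 16-fold, depending on which listed option is used.

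**3. Chance imbalance with no stratification.** The documents do not give the share of women at 29w0d or later, so 30-50% is assumed. For share p, the SD of the between-arm difference is about √[p(1−p) × 2/37]:
- p = 0.3: √(0.21 × 0.0541) = 0.107
- p = 0.4: √(0.24 × 0.0541) = 0.114
- p = 0.5: √(0.25 × 0.0541) = 0.116

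Simulating a single sequence (N = 74, block sizes 2 and 6 equally likely) gives the same SDs, about 11 points. The arms differ by more than 15 points in 16%, 19% and 20% of trials for p = 0.3, 0.4 and 0.5. They differ by 20 points or more in about 6-8%, counting both directions.

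**4. Effect on the treatment contrast.** Shift = imbalance × difference in mean time between bands. The documents do not give that difference, so 2-6 h is assumed. For a 20-point imbalance:
- 0.20 × 2 = 0.4 h
- 0.20 × 4 = 0.8 h
- 0.20 × 6 = 1.2 h

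For comparison, the target is 4 h and the planned standard error is 6 × √(2/37) = 1.39 h.

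**5. Hospital.** On the 60:30 split, the smaller unit would supply about 74/3 ≈ 25 women. The result depends on how the containers are stocked:
- One list used in order of enrolment across both units: arm counts at the smaller unit differ by 6 or more in about 17% of trials.
- The series cut consecutively (for example 1-49 and 50-74): at most one block is broken. A difference of 6 or more did not occur in 10,000 simulated trials, and 4 or more occurred in 0.3%.

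**6. With stratified lists.** The largest block is 6, so the arms cannot differ by more than 3 within a stratum. With four lists (two hospitals × two bands), the SD of the band imbalance falls from about 11 to about 3 points. Arm totals differ by 4 or more in about 12% of simulated trials, and never by more than 8.

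**7. Analysis.** At an assumed 6 h band difference:
- Unstratified lists, unadjusted t-test: type I error about 5%, power about 0.81.
- Four lists, unadjusted t-test: type I error about 2.4-3.2%, power about 0.83.
- Four lists, stratifiers in the model: power about 0.89-0.91.

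The last line can be checked by hand. If one third of women are in one level and the total SD is 6, the residual SD is √(36 − p(1−p)D²). For D = 2, 4 and 6 h this is √35.11 = 5.93, √32.44 = 5.70 and √28 = 5.29. Power at 37 per arm is then 0.83, 0.86 and 0.90.

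**The case against.** The strongest reply is that simple blocked randomisation is already valid. That stands. Both factors are balanced in expectation, and even with bands 6 h apart the unadjusted t-test rejects in about 5% of null trials. A reader might infer from the missing stratification that the arms will be unbalanced, or that the test is biased. Neither follows, because chance imbalance is already part of the test's error rate.

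A reader might also infer that there is one list for both hospitals and that sharing it must break the blocks. The text supports neither inference. It refers to a scheme without saying how many lists it contains, and a consecutive split would keep nearly all blocks whole. The 17% figure for the smaller hospital applies only if one list is used in enrolment order across both units.

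A third tempting reading is that imbalance could by itself produce the 4 h target difference. With bands 6 h apart, that needs an imbalance of 4/6 = 67 points, which did not occur in 30,000 simulated trials. Even the 1.2 h shift is below one standard error.

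It is also fair to say that the documents give no time to delivery by band, and do not say that a lower listed dose means slower delivery. Both hospitals work from one listed protocol, so the argument for hospital is weaker than for gestational age.

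Finally, gestational age is recorded at intake, so covariate adjustment alone would address much of this. That is largely right: in step 7 most of the power gain comes from the analysis. Stratification adds visible balance, and it settles how the containers are stocked.

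**Conclusion.** The point holds as a matter of precision, credibility and an unstated detail, not of validity. Section V names no stratification by hospital or gestational-age band and leaves the list structure for two units open, and section 7.2 adjusts for neither factor. In 74 women, an imbalance of more than 15 points on the 29w0d split has a 16-20% chance. One of 20 points or more has about a 6-8% chance and would move the contrast by 0.4-1.2 h.

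These sizes rest on two assumptions that the documents cannot confirm: 30-50% of women at 29 weeks or later, and a 2-6 h difference in mean time between bands. If the bands hardly differ, little is lost. The missing statement of the list structure needs correcting in any case. Label: cheap improvement.

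**What to change.** In section V, state the list structure. Generate separate permuted-block lists for each hospital and for gestational age below 29w0d versus 29w0d and over, which makes four lists. Label each container with its list, and stock each Pyxis only with its own hospital's two lists, used strictly in order.

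In section 7.2, include hospital and gestational-age band as factors in the primary analysis, for example a linear model beside a stratified rank test. This should go with the stratification, because the unadjusted t-test becomes conservative once allocation is stratified on a factor that predicts the outcome.

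The cost is a new list from the research pharmacy before packing and a few spare packs. Up to four final blocks may be incomplete, so arm totals may differ by a few women. The smallest stratum would be thin: about 25 × 0.30 ≈ 7-8 women if 30% are at 29 weeks or later. The stated sample size of 74 does not change.

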3.1 Study Drug Information

Mifepristone is a 19-nor-steroid derivative of norethindrone that competitively binds to progesterone and glucocorticoid receptors, with antagonist effect. The majority of the drug is absorbed through the gut (70%), it then undergoes demethylation and hydroxylation in P-450 microenzyme systems, namely CYP3A4 [18]. Subsequent monodemethylated, didemethylated and hydroxylated metabolites all maintain significant receptor activity[19]. Mifepristone and its metabolites are bound to alpha 1 acid glycoprotein in serum (AAG); saturation is reached with 100 mg of mifepristone. Peak plasma concentrations are reached within 1-2 hours of ingestion, with rapid distribution, alpha half-life of 1.4 hours, and a long beta half-life, elimination time of 20-30 hours [18]. Dosage regimens of 200 mg or more quickly saturate AAG and with the elaboration of metabolites nonlinear pharmacokinetics results in a large pool of biologically active substrates [19]. The physiologic effects of mifepristone include decidual detachment, necrosis, capillary regression, cervical softening and potentiation of myometrial contractions through the loss of progesterone's inhibitory effects [20]. This profile lends compelling support that mifepristone can confer tissue changes and procedural benefit within hours of administration. Of note, since Mifepristone is mainly metabolized by microenzyme CP3A4, the study will thoroughly review patients' medications/substances that may have the potential to induce/inhibit this enzyme. The safety and toxicity profiles of mifepristone are excellent. The FDA approved regimens for medication abortion in the US includes a dose of 800 mg and does not require any consideration or contraindication for women who are taking cytochrome inducing or inhibiting agents. It is not anticipated that many young, pregnant patients will be on such drugs; however, if a significant difference of patients' intake of such medications is noticed among the study arm compared to the control arm, the analysis of the outcomes will take that into account as a possible confounder, ie. exclude such patients in sub-analysis or control for this as a confounder.

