The hospital staff will maintain medical records as per standard of care. The research team will assign a unique numerical participant identifier with enrollment and allocation of participants. As previously mentioned this identifier will correspond with the information on the sealed medication envelope. Case report forms (CRF) will capture relevant data such as: medication administration time points, clinical events and secondary outcomes. Nursing, pharmacy and medical records will be reviewed to assure accuracy and completeness. Data proofing and collection will be completed by persons blinded to treatment assignment. Intake measures will include: age, socio-economic status, gestational age, method of attainment of gestational age, insurance, gravidity and parity, previous cesarean deliveries, medical history, most recent hemoglobin and hematocrit. Admission data will include cervical exam, membrane intact or rupture status, and vital signs. Secondary outcomes, additional interventions, and adverse events will be captured on the CRF. Due to the fact that participants will be inpatient for the duration of their induction and post-partum course, we do not anticipate any significant withdrawals, deviations or incomplete data sets. Patient identifiers will be secured in locked and protected environments. The CRF and abstracted data will not have any patient identifiers.

VII Statistical Guidelines

7.1 Sample Size:

Based on a review of the literature, institutional charts and clinician experience, the mean time to delivery of fetus is projected to be 24 hours with a standard deviation of 6 hours. To detect a change in 4 hours, with a two-sided alpha of 0.05 and power of 0.8: 37 persons would be needed in each group for a total of 74 persons enrolled in the study. The effect of 4-hour reduction is chosen because it is considered a clinically significant reduction.

7.2 Analysis:

An intention to treat analysis will be completed. Two sample t-test and Wilcoxon rank sum test will be calculated for the primary outcome of time to delivery of fetus. Other secondary outcomes will be described with descriptive statistics and compared with ANOVA or Chi square analysis.

VIII Ethical Consideration

8.1 Confidentiality:

The participants, providers, and research team will all be blinded for the duration of the study. The patients' medical information is protected under HIPAA, therefore only staff directly involved in the

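### The primary comparison is unadjusted although gestational age, parity and cervical exam are collected; a prespecified adjusted model is a cheap possible gain in precision at N = 74, not the repair of an error.

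*Combined protocol and SAP*

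**What the plan says.** Section 7.2 gives the whole analysis of the primary outcome: "An intention to treat analysis will be completed", followed by "Two sample t-test and Wilcoxon rank sum test will be calculated for the primary outcome of time to delivery of fetus". It names no covariate and does not say which of the two tests is primary.

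Section V describes the allocation: "Allocation methods will be variable block randomization". It names no stratification factor.

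Section VI shows that the relevant baseline data will be on file. "Intake measures will include: age, socio-economic status, gestational age, method of attainment of gestational age, insurance, gravidity and parity, previous cesarean deliveries" covers gestational age and parity, and "Admission data will include cervical exam, membrane intact or rupture status, and vital signs" covers the cervix.

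Section 2.1, item 6, lists a different misoprostol schedule for each gestational-age band, and item 6d leaves methods to the physician team. Section 4.3, item 9, excludes women in active labor only above 6 cm, so starting dilation can vary widely.

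The only adjustment mentioned anywhere is in section 3.1. It concerns drugs acting on CYP3A4 and applies only if the arms are seen to differ: "exclude such patients in sub-analysis or control for this as a confounder".

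**The concern.** A small trial with a continuous outcome gains most from baseline variables that predict the outcome. Here three candidates are recorded and not used. Gestational age is linked to the listed induction schedule, and parity and starting dilation are plausible predictors of how long an induction takes. With 74 women and no stratification, the arms can also differ on these factors by chance.

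Whatever part of the outcome variance these factors explain stays in the error term of an unadjusted test. The interval around the 4 h effect is then wider than it need be. Covariates picked after the allocation is known would not be credible, so the choice must be written down beforehand.

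**Working it through.** **Inputs from section 7.1.** "the mean time to delivery of fetus is projected to be 24 hours with a standard deviation of 6 hours"; difference 4 h, two-sided alpha 0.05, power 0.80, 37 per group.

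**Step 1: reproduce the plan's figure.**
- Standard error of the difference = 6 × √(2/37) = 1.395 h.
- Noncentrality = 4 / 1.395 = 2.87 on 72 df; power from the noncentral t is 80.8%.
- The t-based calculation gives 37 per arm, 74 in total, as stated. The normal approximation gives 36 per arm.
- 95% CI half-width = 1.993 × 1.395 = 2.78 h.

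**Step 2: adjusted model in hours, roughly normal times.** Covariates are gestational-age band (2 df), parity 0 v 1 or more (1 df) and dilation in cm (1 df). Residual df = 74 − 2 − 4 = 68. R-squared, the share of within-arm variance explained, is **not in the documents and is assumed**.
- Residual SD = 6 × √(1 − R²).
- Chance imbalance of the covariates between arms raises the variance of the difference by a factor averaging 1 + 4/67 = 1.060. Power was averaged over that imbalance.
- Example at R² = 0.20: residual SD = 6 × √0.80 = 5.37 h; standard error = 5.37 × √(2/37) × √1.060 = 1.285 h; half-width = 1.995 × 1.285 = 2.56 h.

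| Assumed R² | Power | 95% CI half-width |
|---|---|---|
| t-test, unadjusted | 80.8% | 2.78 h |
| 0 | 78.4% | 2.87 h |
| 0.10 | 82.5% | 2.72 h |
| 0.20 | 86.6% | 2.56 h |
| 0.30 | 90.7% | 2.40 h |

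Break-even with the t-test is at R² of about 0.06. It depends on coding: with three single-df terms it is about 0.04.

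**Step 3: does this hold if times are skewed?** The documents give no distribution of times, so shape was varied by simulation: 20,000 trials per cell, 37 per arm, SD 6 h, shift 4 h. Further assumptions were three equal bands, half the women parous, skewed dilation from 0 to 6 cm, and equal shares of R². Power in %, at R² = 0 / 0.10 / 0.20 / 0.30:

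| Residual shape | Wilcoxon | Adjusted, hours | Adjusted, ranks |
|---|---|---|---|
| Normal | 78.8 / 79.0 / 78.7 / 78.9 | 78.4 / 82.5 / 86.6 / 90.7 (from step 2) | 76.5 / 81.0 / 85.0 / 88.8 |
| Mild skew (0.7) | 81.9 / 81.8 / 79.9 / 80.1 | 78.4 / 82.4 / 86.2 / 90.5 | 80.3 / 83.3 / 86.5 / 90.3 |
| Strong skew (1.4) | 90.8 / 87.8 / 85.8 / 84.0 | 78.8 / 82.7 / 86.5 / 90.3 | 89.6 / 90.3 / 92.0 / 93.8 |

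Under strong skew the hours model trails the Wilcoxon test until R² is about 0.19; at R² = 0 the gap is 90.8 − 78.8 = 12.0 points. The adjusted rank model breaks even with the Wilcoxon test at R² of about 0.03 to 0.05 in all three shapes. Its largest loss is 78.8 − 76.5 = 2.3 points. Type I error was 4.5 to 5.2% for all tests where it was checked (normal and strong skew).

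**The case against.** The strongest reply is that this is a preference. The comparison is randomised and blinded, the t-test is valid without covariates, and 74 is the right number for it. All of that stands. A reader might infer that the plan's primary test is biased or underpowered because it ignores these variables; the documents do not support that, and step 1 shows the opposite.

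Second, the benefit rests on an R-squared that nobody has supplied. The documents report no delivery times by band, parity or dilation, and item 6d of section 2.1 means that band need not determine the schedule used. This also stands, which is why the range starts at zero and the break-even is given.

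Third, the hours model is not always the better choice. The planned Wilcoxon test already protects against skew, and replacing it with an hours model alone could lose up to 12 points. This objection changes the recommendation: the adjusted rank model has to be prespecified beside the hours model.

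Fourth, no selection of these covariates after the fact is planned, and section V withholds the allocation scheme until the analysis phase. That is correct. A reader might take the data-dependent rule in section 3.1 as evidence of such selection, but it concerns a different variable. The sealed scheme simply means that the model can still be fixed credibly.

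**Conclusion.** The point holds as something to consider, not as an error. Prespecified adjustment for baseline values already collected could raise power for 4 h from 80.8% to about 86.6% or 90.7% if the covariates explain 20% or 30% of the variance and times are roughly normal. If they explain nothing, it costs about 2 points, whether adjusted hours are set against the t-test or adjusted ranks against the Wilcoxon test. Whether there is a gain, and how large, cannot be told from the documents.

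Two stronger inferences should be resisted. The sample size should not be cut on the strength of an assumed R-squared. Nor does it follow that the hours model improves on both planned tests, since under strong skew it improves on the Wilcoxon test only above an R-squared of about 0.19.

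Section VI says "we do not anticipate any significant withdrawals, deviations or incomplete data sets". How failed inductions and missing covariates are handled is a separate matter and forms no part of this point.

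**What to change.** Amend section 7.2 before unblinding:

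1. Prespecify a linear model of hours to delivery on arm, adjusted for gestational-age band (20w0d-23w6d, 24w0d-28w6d, 29w0d or more), parity (0 v 1 or more) and admission cervical dilation in cm. This is the adjusted counterpart of the t-test on which section 7.1 sizes the trial. Report the adjusted difference in hours with its 95% CI.
2. Prespecify the same covariates in a model on ranks, as the adjusted counterpart of the Wilcoxon test.
3. State in advance which of the two is primary. Use the rank model if the institutional chart data behind section 7.1 show marked right skew.
4. Keep the unadjusted t-test and Wilcoxon test as sensitivity analyses, and keep N at 74.

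**Cost.** SAP wording and no new patients, plus a line on the CRF confirming that the cervical exam records dilation in cm, which section VI does not spell out. The statistical price is the loss of about 2 points if the covariates prove uninformative. The 12-point risk against the Wilcoxon test arises only if the hours model is made primary and times turn out strongly skewed with no prognostic covariates; item 3 is there to limit it.
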